# 18.2. Appendix 2: Elements of Informed Consent

## **ELEMENTS OF INFORMED CONSENT**

Both the informed consent discussion and the written informed consent form and any other written information to be provided to subjects should include explanations of the following:

- That the study involves research.
- The purpose of the study.
- The study treatment(s) and the probability for random assignment to each treatment.
- The study procedures to be followed including all invasive procedures.
- The subject's responsibilities.
- Those aspects of the study that are experimental.
- The reasonably foreseeable risks or inconveniences to the subject and, when applicable, to an embryo, fetus, or nursing infant.
- The reasonably expected benefits. When there is no intended clinical benefit to the subject, the subject should be made aware of this.
- The alternative procedure(s) or course(s) of treatment that may be available to the subject, and their important potential benefits and risks.
- The compensation and/or treatment available to the subject in the event of study-related injury.
- The anticipated prorated payment, if any, to the subject for participating in the study.
- The anticipated expenses, if any, to the subject for participating in the study.
- That the subject's participation in the study is voluntary and that the subject may refuse to participate or withdraw from the study, at any time, without penalty or loss of benefits to which the subject is otherwise entitled.
- That the monitor(s), the auditor(s), the IRB/IEC, and the regulatory authority(ies) will be granted direct access to the subject's original medical records for verification of clinical study procedures and/or data, without violating the confidentiality of the subject, to the extent permitted by the applicable laws and regulations and that, by signing a written informed consent form, the subject or the subject's legally acceptable representative is authorizing such access.
- That records identifying the subject will be kept confidential and, to the extent permitted by the applicable laws and/or regulations, will not be made publicly available. If the results of the study are published, the subject's identity will remain confidential.

- That the subject or the subject's legally acceptable representative will be informed in a timely manner if information becomes available that may be relevant to the subject's willingness to continue participation in the study.
- The person(s) to contact for further information regarding the study and the rights of study subjects, and whom to contact in the event of study-related injury.
- The foreseeable circumstances and/or reasons under which the subject's participation in the study may be terminated.
- The expected duration of the subject's participation in the study.
- The approximate number of subjects involved in the study.

DLCO	diffusing capacity of the lung for carbon monoxide
ECG	Electrocardiogram
eCRF	electronic case report form
EDSS	Expanded Disability Status Scale
FEV 1	forced expiratory volume at 1 second
FS	Functional System
FVC	forced vital capacity
GdE	gadolinium enhancing
GGT	gamma glutamyltransferase
HDL	high-density lipoprotein
IFN	interferon
IFN β-1a	interferon beta-1a
IM	intramuscular(ly)
ITT	intent-to-treat
IVRS	Interactive Voice Response System
LCLA	low-contrast letter acuity
LFT	liver function test
LOCF	last observation carried forward
MCH	mean corpuscular hemoglobin
MCHC	mean corpuscular hemoglobin concentration
MCV	mean corpuscular volume
MSFC	Multiple Sclerosis Functional Composite
MRI	magnetic resonance imaging
MS	multiple sclerosis
MSQOL-54	Multiple Sclerosis Quality of Life-54
NRI	non-responder imputation
OCT	optical coherence tomography
PD	pharmacodynamic(s)
PFT	pulmonary function test
PK	pharmacokinetic(s)
PP	per protocol
QD	once daily
QW	once weekly
RBC	red blood cell

RMS	relapsing multiple sclerosis	
S1P1R	sphingosine 1-phosphate 1 receptors	
SAE	serious adverse event	
SAP	statistical analysis plan	
SBP	systolic blood pressure	
SD	standard deviation	
SDMT	Symbol Digit Modalities Test	
SGOT	serum glutamic oxaloacetic transaminase	
SGPT	serum glutamic pyruvic transaminase	
ULN	upper limit of normal	
WBC	white blood cell	

#### 1. ADMINISTRATIVE STRUCTURE

This study is being conducted under the sponsorship of Receptos, Inc. The clinical monitoring, data management and statistical analysis are being performed under contract with , in collaboration with Receptos, Inc.

### 1.1. Data Quality Assurance

The Clinical, Data Management, and Biostatistics departments at will work diligently and collaboratively, internally and with the sponsor, to ensure that the data collected and analyzed for this study are of the highest quality possible. This will be accomplished in part by having thorough edit checks written, programmed, and updated as needed to guarantee high quality data. Edit checks will be reviewed by the statistician, programmer and other team members on an ongoing basis to evaluate whether any checks need to be added or any existing checks need to be modified.

All analyses will be conducted using SAS® Version 9.1 or higher.

#### 2. INTRODUCTION

RPC01-201 is a phase 2/3 clinical trial consisting of a 24-week placebo-controlled (Part A, phase 2) trial and a 24-month active-controlled (Part B, phase 3) trial of RPC1063 versus interferon (IFN)  $\beta$ -1a in patients with relapsing multiple sclerosis (RMS). The Part A, phase 2 portion of the study characterizes the short-term efficacy and safety profile of RPC1063 on improving disease activity as measured by magnetic resonance imaging (MRI) parameters over 24-weeks of treatment. The Part B, phase 3 portion of the study characterizes the efficacy and safety profile of RPC1063 on clinical outcomes (e.g., relapse rate and disability progression) in RMS patients treated for 24 months.

The analysis of the Part A portion of the study is covered under a separate statistical analysis plan (SAP). This SAP describes the statistical methods to be used during the reporting and analysis of clinical data collected in Part B of the study. All objectives, endpoints, and analysis methods described below apply to the Part B portion of the study only. This plan should be read in conjunction with the study protocol and the case report forms (CRFs).

### 3. OBJECTIVES

The primary objective is:

• To assess whether the clinical efficacy of RPC1063 is superior to IFN  $\beta$ -1a in reducing the rate of clinical relapses at the end of Month 24 in patients with RMS

The secondary objectives of are:

- To assess the effect of RPC1063 on the proportion of patients with new/enlarging T2 lesions at Month 24
- To evaluate whether the efficacy of RPC1063 is superior to IFN β-1a in delaying the accumulation of disability, as assessed by the Multiple Sclerosis Functional Composite (MSFC), and visual function as measured by the low-contrast letter acuity test (LCLA)
- To evaluate whether the efficacy of RPC1063 is superior to IFN β-1a in delaying the accumulation of disability, as assessed by the Expanded Disability Status Scale (EDSS)
- To assess the effect of RPC1063 on brain atrophy over 24 months
- To evaluate the effect of RPC1063 on patient-reported quality of life as assessed by the Multiple Sclerosis Quality of Life-54 (MSQOL-54)
- To assess the safety and tolerability of RPC1063 in patients with RMS

The exploratory objectives are:

•

### 4. INVESTIGATIONAL PLAN

[figure not shown]
## 4.1. Overall Study Design and Plan

RPC01-201 Part B is a multi-center, randomized, double-blind, double-dummy, active-controlled parallel group study (Figure 1) of oral RPC1063 in adult patients with RMS. Approximately 1200 patients who meet eligibility criteria during the 30-day screening period will be randomly assigned 1:1:1 to receive one of the three following regimens for 24 months:

- IFN β-1a 30 μg intramuscular (IM) weekly
- RPC1063 0.5 mg oral capsule daily
- RPC1063 1 mg oral capsule daily

The randomization will be stratified by Baseline EDSS category ( $\leq 3.5, > 3.5$ ) and country. It is anticipated that the study will be performed at approximately 200 sites in North America and Eastern and Western Europe.

Figure 1. Study Schematic

### 4.2. Study Endpoints

The primary efficacy endpoint is:

• Annualized relapse rate (ARR) at the end of Month 24

The key secondary efficacy endpoints (rank ordered) are:

- 1. The number of new or enlarging hyperintense T2-weighted brain MRI lesions over 24 months
- 2. The number of GdE brain MRI lesions at Month 24
- 3. Time to onset of disability progression as defined by a sustained worsening in EDSS of 1.0 points or more, confirmed after 3 months and after 6 months

The other secondary endpoints are:

- Proportion of patients who are GdE lesion-free at Month 24
- Proportion of patients who are new or enlarging T2 lesion-free at Month 24
- Percent change in normalized brain volume (atrophy) on MRI scans from Baseline to Month 24
- Change in MSFC score from Baseline to Month 24 (including the lowcontrast letter acuity test [LCLA] measurement of visual function as a component)
- Change in MSQOL-54 score from Baseline to Month 24

The exploratory endpoints are:

Confidential

### 5. GENERAL STATISTICAL CONSIDERATIONS

Statistical testing for the primary efficacy endpoint will be made between each RPC1063 group and the IFN  $\beta$ -1a group (2 treatment contrasts). To account for multiple comparisons, each of the 2 treatment comparisons will be tested at the alpha = 0.025 level.

To control for type 1 error, the 3 key secondary endpoints will be tested in order in a sequential, that ranks the RPC1063 1 mg dose above the RPC1063 0.5 mg dose and the key secondary endpoints in the order shown in section 4.2. If both doses are significant on the primary endpoint, then the first comparison on the key secondary endpoints will be between the RPC1063 1 mg group and the IFN  $\beta$ -1a group at the 5% level of significance. If that comparison is successful, then the same endpoint will be tested for the RPC1063 0.5 mg group vs. the IFN  $\beta$ -1a group comparison at the 5% level of significance. This procedure (Figure 2A) will continue down the rank ordered key secondary endpoint list until a comparison fails to reach statistical significance,

For the 3rd key secondary endpoint of time to onset of sustained disability progression, the data from this study will also be pooled with the data from another phase 3 study, RPC01-301, for hypothesis testing. This pooling will be described in a separate pooling plan.

If only 1 RPC1063 dose is significant on the primary endpoint, then on the rank ordered key secondary endpoint list for the surviving dose only, at the 2.5% level of significance for each key secondary endpoint (Figure 2B).

Figure 2.

Other secondary endpoint analyses will not include adjustments made for multiple comparisons and multiple endpoints.

Unless specified otherwise, all statistical analyses will be performed using a two-sided hypothesis test at the overall 5% level of significance. All p-values will be rounded to four decimal places. If a p-value is less than 0.0001, it will be reported as "<0.0001". If a p-value is greater than 0.9999, it will be reported as ">0.9999".

Continuous data will be presented using descriptive statistics: n, mean, standard deviation (SD), median, minimum and maximum. Categorical data will be summarized by the number and percent. Confidence intervals (CIs) will be 95% and two-sided, unless otherwise stated. Data will be displayed in all listings sorted by treatment group and subject number. When count data are presented, the percent will be suppressed when the count is zero in order to draw attention to the non-zero counts. A row denoted "Missing" will be included in count tabulations where necessary to account for dropouts and missing values. The denominator for all percentages will be the number of patients in that treatment within the population of interest, unless otherwise stated. Non-zero percentages will be rounded to one decimal place, except 100% will be displayed without any decimal places. Additional rounding rules are as follows:

- If the original value has 0 decimal places: mean, median, and CIs will have one decimal place and SD will have 2 decimal places
- If the original value has 1 decimal place: mean, median, and CIs will have 2 decimal places and SD will have 3 decimal places
- If the original value has 2 or more decimal places: mean, median, CIs, and SD will all have 3 decimal places

Minimum and maximum will always have the same decimal places as the original measure, up to a maximum of 3 decimal places.

Subgroup analysis will be performed for the primary and secondary efficacy endpoints where applicable. The following are the pre-defined subgroups:

- Baseline EDSS score (EDSS  $\leq$  3.5 vs. EDSS > 3.5)
- Baseline presence of Gd-enhancing lesions (present vs. absent)
- Prior treatment status (treatment naïve vs. previously treated)
- age at Baseline (age  $\leq 40$  vs. age > 40)
- sex (female vs. male)
- race (white vs. non-white)
- weight (< median vs.  $\ge$  median)

- number of relapses in the past 12 months ( $< 2, \ge 2$ ) for ARR endpoint only
- regions (North America, Western Europe, Eastern Europe)

Any subgroup that does not have at least 5% of the overall sample size (approximately 60 patients) will not be included in subgroup analyses.

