### 5.1. Sample Size

Approximately 1200 patients with RMS will be randomized in this study (approximately 400 per treatment group). The primary analyses will compare the ARRs in each of the RPC1063 groups to the IFN  $\beta$ -1a group using a Poisson regression model at the alpha = 0.025 level. The control ARR is assumed to be equal to 0.3 (Mikol, 2008). Assuming extra-Poisson variation ( $\sigma^2$ =1.3) (Polman, 2011) and at least 12 months of follow-up per patient, the method of Nicholas (Nicholas, 2011) results in a total sample size of 1059 patients (353 per arm) in order to provide 80% power to detect a 43% reduction in the ARR (i.e., an ARR of 0.17 for RPC1063). To account for an assumed dropout rate of approximately 12%, approximately 1200 patients (400 per treatment group) will be enrolled.

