# 7. DEMOGRAPHICS, MEDICAL HISTORY AND BASELINE CHARACTERISTICS

### 7.1. Demographics

The demographics and baseline characteristics will be presented in tables. The demographic characteristics consist of age, age category, sex, race, ethnicity, weight, weight category, height, body mass index, and region. A patient's age in years is calculated using the date of the informed consent and date of birth, or recorded directly on the eCRF. Age will be summarized using the descriptive statistics. The number and percentage of patients in each age category (18-19, 20-29, 30-39, 40-49, 50-55, and >55, as well as <40, ≥40), and in each race category (White, Black, Asian, American Indian or Alaska Native, Native Hawaiian or Other Pacific Islander, and Other) will be reported. The demographics and baseline characteristics summaries will be presented for both ITT and PP populations.

Demographics and baseline characteristics data will be listed.

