### Definition of relapse rate

The relapse rate for each treatment group will be calculated as the total number of relapses experienced in the group divided by the total number of days in the study for the group, and multiplied by 365.25. This is called the unadjusted relapse rate and it will be reported for each treatment group.

The relapse rate for each patient will be calculated as the number of relapses for an individual patient divided by the number of days that patient participated in the study, and multiplied by 365.25. Summary statistics of the individual relapse rate for each treatment group will be reported.

Primary Analysis method – annualized relapse rate

All relapses will be identified as confirmed or unconfirmed prior to database lock. The primary analysis of ARR will be performed using a Poisson regression model. The model will compare treatment groups, adjusted for region, age at Baseline, and the Baseline number of GdE lesions, and will include the natural log transformation of time on study as an offset term. The adjusted relapse rates and their associated 95% CIs, the rate ratios and their associated 95% CIs, and p-values will be reported.

The primary analysis will be repeated in each of the pre-specified subgroups shown in section 5. Forest plots showing the rate ratios and 95% CI for the overall result and the results in each subgroup will be constructed.

Relapse results will be listed.

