#### 9.2.1. Analysis

# **Key Secondary Endpoint: The number of new or enlarging hyperintense T2-weighted brain MRI lesions over 24 months**

The primary analysis of the number of new or enlarging T2 hyperintense lesions over 24 months will be performed using a negative binomial regression model adjusted for region, age at Baseline, and Baseline number of GdE lesions, and will include the natural log transformation of the number of available MRI scans as an offset term. The odds ratios and their associated 95% CIs, relative reductions, and p-values will be reported.

The analysis will be repeated in each of the pre-specified subgroups shown in section 5. Forest plots showing the odds ratios and 95% CIs for the overall result and the results in each subgroup will be constructed.

Three sensitivity analyses will be performed: the first will repeat the primary T2 analysis using the mean number of T2 lesions from patients from the same treatment group to impute missing T2 values. The second will repeat the primary T2 analysis using last observation carried forward (LOCF) method for imputing missing T2 data values. Only data from post-Baseline MRI scans can be carried forward to subsequent timepoints for this analysis. The third will repeat the primary T2 analysis using only patients with complete T2 data at the relevant MRI visits (observed cases analysis). All three sensitivity analyses will include the natural log transformation of exposure time on study (instead of the number of available MRI scans) as the offset term.

All T2 lesion results will be listed.

#### Key Secondary Endpoint: The number of GdE brain MRI lesions at Month 24

The number of GdE brain MRI lesions at Month 24 will be analyzed using a negative binomial regression model adjusted for region, age at Baseline, and Baseline number of GdE lesions, and will include the natural log transformation of the number of available MRI scans as an offset term. The odds ratios and their associated 95% CIs, relative reductions, and p-values will be reported.

The analysis will be repeated in each of the pre-specified subgroups shown in section 5. Forest plots showing the odds ratios and 95% CIs for the overall result and the results in each subgroup will be constructed.

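### Subgroup effects on relapse rate and lesion counts are assessed by refitting the model within each level, with no treatment-by-subgroup interaction to show whether effects differ

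*SAP*

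**What the plan says.** SAP section 5 sets the scope: "Subgroup analysis will be performed for the primary and secondary efficacy endpoints where applicable". It lists eight two-level factors (EDSS, GdE presence, prior treatment, age, sex, race, weight, relapse history) and a three-level region factor. Relapse history is reserved for ARR. That gives 8 × 2 + 3 = 19 levels for ARR and 7 × 2 + 3 = 17 for other endpoints. Levels holding under 5% of the sample, about 60 patients, are dropped.

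For ARR, section 9.1.1 says: "The primary analysis will be repeated in each of the pre-specified subgroups shown in section 5". For each of the two lesion-count endpoints, section 9.2.1 says: "The analysis will be repeated in each of the pre-specified subgroups shown in section 5". In all three cases the named output is a forest plot of ratios and 95% confidence intervals, with the overall result alongside. No such instruction is given for disability progression or the other secondary endpoints, so only the general sentence in section 5 covers them.

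Neither the SAP nor the protocol contains a treatment-by-subgroup term, a heterogeneity test, a significance level for subgroups, or a statement that subgroup results are descriptive. The default in section 5 is that, unless specified otherwise, "all statistical analyses will be performed using a two-sided hypothesis test at the overall 5% level of significance".

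**The concern.** The question a subgroup analysis answers is whether the effect differs between levels. Separate fits answer another question: whether the effect is detectable in each level alone. Each level holds only part of the sample, so its power is lower, and one level can reach significance while its complement does not even when the effects are identical.

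The analysis being repeated reports p-values, and a 95% interval that excludes or includes 1 conveys the same message. Nothing in the plan warns against reading the results this way, and no planned statistic shows whether an apparent difference exceeds chance. What is at stake is a mistaken statement that the drug works in one group and not in another. The confirmatory conclusions are not affected.

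**Working it through.** **Inputs.** SAP section 5.1: "The control ARR is assumed to be equal to 0.3" per year; 0.17 on RPC1063; dispersion 1.3; at least 12 months of follow-up; 353 per arm; 80% power. SAP section 5: "each of the 2 treatment comparisons will be tested at the alpha = 0.025 level". Protocol section 13.2: 0.30 versus 0.19, 24 months, dispersion 1.3, 333 per arm, 90% power. Planned enrolment is about 400 per arm. The subgroup shares are not in the documents, so splits from 50/50 to 95/5 are assumed.

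**Reproducing the plan's sample sizes.** n = (z₁₋α/₂ + z_power)² × 1.3 × (1/(λ₀t) + 1/(λ₁t)) / [ln(λ₁/λ₀)]².
- SAP: (2.241 + 0.842)² × 11.980 / 0.568² = 353.0. Stated: 353.
- Protocol: (2.241 + 1.282)² × 5.588 / 0.457² = 332.4, rounded up to 333. Stated: 333.

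The standard error is therefore the one the plan used: SE = √[1.3 × (1/(nλ₀t) + 1/(nλ₁t))].

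**Discordance under a uniform effect.** A level holding share f of each arm has z_f = z_overall × √f and power about Φ(z_f − 1.96) at the two-sided 5% level, which matches a 95% interval excluding 1. Complementary levels contain different patients, so P(exactly one significant) = p₁(1 − p₂) + p₂(1 − p₁).

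For example, the SAP design has SE = 0.184 and overall z = 0.568/0.184 = 3.08. Each half has z = 2.18 and power 0.587, so discordance is 2 × 0.587 × 0.413 = 0.485.

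| Design (per arm, follow-up, RPC1063 ARR) | Overall z | Power in each half | 50/50 | 70/30 | 85/15 |
|---|---|---|---|---|---|
| 353, 12 months, 0.17 (SAP) | 3.08 | 0.59 | 49% | 55% | 67% |
| 333, 24 months, 0.19 (protocol) | 3.53 | 0.70 | 42% | 51% | 68% |
| 400, 24 months, 0.19 | 3.87 | 0.78 | 34% | 45% | 66% |
| 400, 24 months, 0.17 (most favourable) | 4.64 | 0.91 | 17% | 29% | 56% |

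The last three columns give the chance of discordance per factor and dose. At 0.025 the 50/50 figures become 50%, 48%, 43% and 25%.

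**All nine ARR factors.** Over-dispersed counts were simulated with eight independent two-level factors and three regions, 2,000 runs per scenario. At least one factor was significant in some levels but not all in 92–97% of trials at the SAP design and 89–99% at the protocol design. In the most favourable case the figure was 62–75% with even splits and 99% or more with the assumed uneven splits. The average number of such factors was 4.7–5.4 of 9 at the SAP design and 1.8–4.4 in the most favourable case.

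**Interaction test for comparison.** Under a uniform effect it errs 5% of the time per factor. Over nine factors treated as independent, P(at least one) = 1 − 0.95⁹ = 37%. With an even split, each half has variance 2 × SE², so the difference has standard error √(2 + 2) × SE = 2 × SE. An interaction as large as the design effect then has z = 3.08/2 = 1.54 and power of about 34% at the SAP design.

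**The case against.** The strongest reply is that the SAP never says a subgroup effect will be declared from within-subgroup significance. It sets no subgroup decision rule, and its formal error control covers only the primary and three key secondary endpoints. The forest plots let a careful reader compare ratios. Because complementary levels contain different patients, an approximate heterogeneity test can be worked out from the plotted estimates and intervals. All of this stands. It makes the gap one of reporting and interpretation, but it leaves the reader to derive the one statistic that answers the question.

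A reader might infer that a uniform effect will usually look present in one level and absent in its complement. That is not supported for any given pair: an even split is discordant in under half of trials at 5%, and the chance passes half mainly when splits are uneven. It is likely only that at least one factor shows the pattern.

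A reader might also apply 19 levels and 19 × 2 = 38 dose contrasts to every endpoint. That count is for ARR alone. It is at most 17 levels and 34 contrasts elsewhere, possibly fewer after the 5% rule, and explicit refitting is specified only for ARR, T2 and GdE.

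Two further points change no result. Region is constant within a region, and baseline GdE count is zero in the GdE-absent level, but such a covariate simply drops out of that fit. The roughly 60-patient limit is a floor for inclusion, not an expected subgroup size.

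Finally, the interaction test is weak and produces false signals of its own. That is a reason to label it descriptive, not to omit it.

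**Conclusion.** The point holds as a cheap improvement to the analysis plan. For ARR, T2 and GdE the plan produces subgroup estimates but no assessment of whether they differ. On ARR, with an identical effect in all patients, an evenly split factor misleads a reader who looks at significance in about 17–49% of trials per dose, against about 5% for an interaction test. Over the nine ARR factors at least one misleading pattern is likely in every scenario tried.

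These figures assume the subgroup shares shown, independent factors, the same control rate in every level, standard errors that allow for the 1.3 dispersion, and a 5% reading of subgroup results. The documents give neither the shares nor a subgroup level. The arithmetic is for ARR only; no corresponding figure was derived for the lesion counts. The documents do not support the inference that the sponsor intends to claim subgroup effects from separate p-values, or that the primary conclusion is at risk.

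**What to change.** In SAP sections 5, 9.1.1 and 9.2.1, keep the forest plots and the separate fits behind them. For each factor, also fit one model to the full ITT population with the primary covariates plus subgroup and treatment-by-subgroup terms. Beside each plot, print for each dose the interaction estimate (a ratio of ratios), its 95% confidence interval and its p-value; for region, add a joint test over the three levels. State that subgroup results are descriptive and that significance within a level will not be interpreted. State also which of the remaining secondary endpoints the general sentence in section 5 is meant to cover.

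As a minor tidy-up, use one age cut. Section 5 puts patients aged exactly 40 in the younger group, while section 7.1 tabulates "18-19, 20-29, 30-39, 40-49, 50-55, and >55, as well as <40" and its complement, which puts them in the older one.

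The cost is SAP wording and modest programming, with no change to data, design or sample size. The price is the low power and the roughly 37% chance of at least one false interaction over nine factors shown above, hence the descriptive label.
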